7.1. Study Subjects

7.1.1. Disposition of Subjects

Subjects disposition will be summarized, including the number of subjects enrolled, attempted implant, implanted, died, explanted, withdrawn, lost-to follow up, and completed each visit during the study.

7.1.2. Clinical Investigation Plan (CIP) Deviations

Protocol violations (study deviations) will be reported to Medtronic throughout the study by each site and identified through monitoring activities.

Deviations will be summarized by type for each interval. The percent of subjects with the deviations will be calculated based on the number of subjects eligible for the specified visit (eg., screening, enrollment, index procedure).

7.1.3. Analysis Sets

All subjects with severe aortic stenosis and bicuspid anatomy who provide an informed consent will be considered screened and enrolled and all available data will be entered into the Electronic Data Capture (EDC) system.

There are two different analysis sets that are defined for this study. The primary analysis will be the “attempted implant” analysis. Analysis sets used for each objective are defined under the corresponding objective section. The analysis subsets are defined below.

Attempted implant set: The attempted implant set consists of all enrolled subjects with an attempted implant procedure, defined as when the subject is brought into the procedure room and any of the following have occurred: anesthesia administered, vascular line placed, TEE placed or any monitoring line placed. Day 0 is date of first attempted procedure.

Implanted set: The Implanted set consists of all the attempted implant subjects who are actually implanted with the TAV. Day 0 is date of first attempted procedure.

All data collected from enrolled, attempted implant, and implanted subjects will be utilized in the analyses as appropriate. Analyses of the primary and additional endpoints will be descriptive, and no statistical hypothesis tests will be performed.

7.2. General Methodology

Descriptive statistics will be used to report study data. For continuous variables (eg. age), the mean, median, standard deviation, minimum, maximum and interquartile ranges (IQR) will be presented. For categorical variables, the number and percentage of subjects in the category of interest will be presented.

For time to event variables, Kaplan-Meier analyses of event rates at 30 days, 1 year and annually through end of study will be presented. For these analyses, the time points will correspond to 30 days, 365 days, 730 days, 1095 days, 1460 days, 1825 days, 2190 days, 2555 days, 2920 days, 3285 days and 3650 days post implantation respectively. At each time point with data, the product limit estimate of the event, the number of subjects at risk, the number of subjects with events, and the 95% confidence interval will be presented. For subjects without an event, the date of censoring will be the latest date of all follow-up visits, assessments, and events (including death).

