### **12.7. Additional Outcome Measures**

Additional Outcome Measures are listed as follows:

1. All-cause mortality at one year, and annually through 10 years
2. All stroke (disabling and non-disabling) at one year, and annually through 10 years
3. New permanent pacemaker implantation at 30 days
4. Myocardial Infarction at 30 days
5. Life-threatening bleeding at one year, and annually through 10 years
6. Prosthetic valve endocarditis at one year, and annually through 10 years
7. Prosthetic valve thrombosis at one year, and annually through 10 years
8. Valve-related dysfunction requiring repeat procedure at one year, and annually through 10 years
9. Repeat hospitalization for ascending aorta disease at 30 days, one year, and annually through 10 years
10. Repeat hospitalization for aortic valve disease at one year, and annually through 10 years
11. Hemodynamic performance metrics by Doppler echocardiography
  - Mean aortic gradient at baseline, 30 days, one year, and annually through 10 years
  - Effective orifice area at baseline, 30 days, one year, and annually through 10 years
  - Degree of total, peri, and transvalvular prosthetic regurgitation at baseline, 30 days, one year, and annually through 10 years
12. New York Heart Association (NYHA) functional classification at baseline, 30 days, one year and annually through 10 years
13. Health-related quality of life as assessed by

- Kansas City Cardiomyopathy (KCCQ) instrument at baseline, 30 days, one year, annually through 5 years
- EQ-5D survey at baseline, 30 days and one year

Analyses of the additional endpoints will be descriptive. Attempted implant set will be used for safety and quality of life outcomes. However, the hemodynamic performance outcomes will be analyzed for the implanted set. Continuous variables will be summarized as the number of subjects, means, standard deviations, medians, minimums, maximums, and interquartile ranges. Categorical variables will be summarized as frequencies and percentages. A Kaplan-Meier estimate will be performed for time-to-event analysis.

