**1.0 Safety Endpoints (continued)**

Stroke and TIA

Diagnostic criteria
 
1) Acute episode of a focal or global neurological deficit with at least 1 of the following:
 
 
• change in the level of consciousness
 
• hemiplegia, hemiparesis
 
• numbness or sensory loss affecting 1 side of the body
 
• dysphasia or aphasia
 
• hemianopia
 
• amaurosis fugax
 
• other neurological signs or symptoms consistent with stroke
 
 
Stroke: duration of a focal or global neurological deficit <math>\geq 24</math> h; OR <math>< 24</math> h if available neuroimaging documents a new hemorrhage or infarct; OR the neurological deficit results in death
 
TIA: duration of a focal or global neurological deficit <math>< 24</math> h, any variable neuroimaging does not demonstrate a new hemorrhage or infarct
 
2) No other readily identifiable non-stroke cause for the clinical presentation (eg, brain tumor, trauma, infection, hypoglycemia, peripheral lesion, pharmacological influences), to be determined by or in conjunction with the neurologist
 
3) Confirmation of the diagnosis by at least 1 of the following:
 
 
• Neurologist or neurosurgical specialist
 
• Neuroimaging procedure (CT scan or brain MRI), but stroke may be diagnosed on clinical grounds alone
 

Stroke Definitions
 
Disabling stroke: an mRS score of 2 or more at 90 days and an increase in at least 1 mRS category from an individual’s pre-stroke baseline
 
Non-disabling stroke: an mRS score of <math>< 2</math> at 90 days or one that does not result in an increase in at least 1 mRS category from an individual’s pre-stroke baseline

Stroke Classifications
 
Ischemic: an acute episode of focal cerebral, spinal, or retinal dysfunction caused by infarction of the central nervous system tissue
 
Hemorrhagic: an acute episode of focal or global cerebral or spinal dysfunction caused by intraparenchymal, intraventricular, or subarachnoid hemorrhage
 
Undetermined: insufficient information to allow categorization as ischemic or hemorrhagic

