## 2.0 Other Related Complications (continued)

Bleeding Complications	
Life-threatening or disabling bleeding	1) Fatal bleeding ( BARC type 5 ) OR 2) Bleeding in a critical organ, such as intracranial, intraspinal, intraocular, or pericardial necessitating pericardiocentesis, or intramuscular with compartment syndrome ( BARC type 3b and 3c ) OR 3) Bleeding causing hypovolemic shock or severe hypotension requiring vasopressors or surgery ( BARC type 3b ) OR 4) Overt source of bleeding with drop in hemoglobin $\geq 5$ g/dL or whole blood or packed red blood cells (RBCs) transfusion $\geq 4$ units* ( BARC type 3b )
Major bleeding ( BARC type 3a )	1) Overt bleeding either associated with a drop in the hemoglobin level of at least 3.0 g/dL or requiring transfusion of 2 or 3 units of whole blood/RBC, or causing hospitalization or permanent injury, or requiring surgery AND 2) Does not meet criteria of life-threatening or disabling bleeding
Minor bleeding ( BARC type 2 or 3a, depending on the severity )	Any bleeding worthy of clinical mention (eg, access site hematoma) that does not qualify as life-threatening, disabling, or major
*Given one unit of packed RBC typically will raise hemoglobin concentration by 1 g/dL, an estimated decrease in haemoglobin will be calculated; BARC: Bleeding Academic Research Consortium  ; RBC: red blood cell	

Note: With respect to blood transfusions, it is critical to acknowledge that a bleeding complication has to be the result of overt bleeding and cannot be adjudicated based on blood transfusions alone.

Acute Kidney Injury (up to 7 days post procedure)	
Stage 1	1) Increase in serum creatinine to 150%-199% (1.5-1.99 x increase compared with baseline) OR increase of $\geq 0.3$ mg/dL ( $\geq 26.4$ mmol/L) OR 2) Urine output $< 0.5$ mL/kg/h for $> 6$ but $< 12$ h
Stage 2	1) Increase in serum creatinine to 200%-299% (2.0-2.99 x increase compared with baseline) OR 2) Urine output $< 0.5$ mL/kg/h for $> 12$ but $< 24$ h
Stage 3	1) Increase in serum creatinine to $\geq 300\%$ ( $> 3$ x increase compared with baseline) OR serum creatinine of $\geq 4.0$ mg/dL ( $\geq 354$ mmol/L) with an acute increase of at least 0.5 mg/dL (44 mmol/L) OR 2) Urine output $< 0.3$ mL/kg/h for $\geq 24$ h OR 3) Anuria for $\geq 12$ h

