7.4. Handling of Missing, Unused, and Spurious Data and Dropouts

Every effort will be undertaken to minimize missing data. In time-to-event outcomes drop-outs will be censored at the time of discontinuation, consistent with the Kaplan-Meier approach.

Missing (accidentally, due to withdrawal, missing follow-up or loss to follow-up, etc.), unused and spurious data will remain identifiable in the database. Data from subjects that cannot be analyzed for a specific variable will be displayed as missing in the relevant summary tables. In this manner, all data for a specific variable are accounted for. Unless otherwise specified, no statistical techniques will be used to impute missing data. The number of subjects included in each analysis will be reported so that the reader can assess the potential impact of missing data.

In the case of partial dates, if only the month and year are known, the event or assessment will be analyzed as if it occurred on the 15th of that month. If only the year is known, the event or assessment will be analyzed as if it occurred on June 30th of that year. These resolutions of partial dates are subject to the restrictions that events must occur no earlier than the procedure date.

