7.9.3. Additional Outcome Measures

1. All-cause mortality at one year, and annually through 10 years

Event rate estimates will be provided at 1 year and annually thereafter up to 10 years for the attempted implant set. The outcome is descriptive including Kaplan-Meier rates and no statistical hypothesis test is specified.

2. All stroke (disabling and non-disabling) at one year, and annually through 10 years

Event rate estimates will be provided at 1 year and annually thereafter up to 10 years for the attempted implant set. The outcome is descriptive including Kaplan-Meier rates and no statistical hypothesis test is specified.

3. New permanent pacemaker implantation at 30 days

Event rate estimates will be provided at 30 days for the attempted implant set. The outcome is descriptive including Kaplan-Meier rates and no statistical hypothesis test is specified.

4. Myocardial Infraction at 30 days

Event rate estimates will be provided at 30 days for the attempted implant set. The outcome is descriptive including Kaplan-Meier rates and no statistical hypothesis test is specified.

5. Life-threatening bleeding at 30 days, one year, and annually through 10 years

Event rate estimates will be provided at 30 days, 1 year and annually thereafter up to 10 years for the attempted implant set. The outcome is descriptive including Kaplan-Meier rates and no statistical hypothesis test is specified.

6. Prosthetic valve endocarditis at 30 days, one year, and annually through 10 years

Event rate estimates will be provided at 30 days, 1 year and annually thereafter up to 10 years for the attempted implant set. The outcome is descriptive including Kaplan-Meier rates and no statistical hypothesis test is specified.

7. Prosthetic valve thrombosis at 30 days, one year, and annually through 10 years

Event rate estimates will be provided at 30 days, 1 year and annually thereafter up to 10 years for the attempted implant set. The outcome is descriptive including Kaplan-Meier rates and no statistical hypothesis test is specified.

8. Valve-related dysfunction requiring repeat procedure at 30 days, one year, and annually through 10 years

Event rate estimates will be provided at 30 days, 1 year and annually thereafter up to 10 years for the attempted implant set. The outcome is descriptive including Kaplan-Meier rates and no statistical hypothesis test is specified.

9. Repeat hospitalization for ascending aorta disease at 30 days, one year, and annually through 10 years

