Event rate estimates will be provided at 30 days, 1 year and annually thereafter up to 10 years for the attempted implant set. The outcome is descriptive including Kaplan-Meier rates and no statistical hypothesis test is specified.

10. Repeat hospitalization for aortic valve disease at 30 days, one year, and annually through 10 years

Event rate estimates will be provided at 30 days, 1 year and annually thereafter up to 10 years for the attempted implant set. The outcome is descriptive including Kaplan-Meier rates and no statistical hypothesis test is specified.

11. Hemodynamic performance metrics by Doppler echocardiography
 - a. Mean aortic gradient at baseline, 30 days, one year, annually through 5 years and at years 7 and 10
 - b. Effective orifice area at baseline, 30 days, one year, annually through 5 years and at years 7 and 10
 - c. Degree of total, peri, and transvalvular prosthetic regurgitation at baseline, 30 days, one year, annually through 5 years and at years 7 and 10

The echocardiographic measurements will be reported at each of the specified time points for the implanted set with Echo data. No statistical hypothesis test is specified.

For mean gradient and effective orifice area, the descriptive statistics (mean, median, standard deviation, minimum, maximum and interquartile ranges) will be presented.

Prosthetic regurgitation severity will be reported as proportions at each specified time point.

12. New York Heart Association (NYHA) functional classification at baseline, 30 days, one year and annually through 5 years and at years 7 and 10

NYHA classifications will be summarized with frequencies and percentages at baseline, 30 days, 1 year, and annually through 5 years and at years 7 and 10. All attempted implant subjects with available NYHA collections (I/II/III/IV) will be included in the analysis. No statistical hypothesis test is specified.

13. Health-related quality of life as assessed by
 - a. Kansas City Cardiomyopathy (KCCQ) instrument at baseline, 30 days, one year, annually through 5 years
 - b. EQ-5D survey at baseline, 30 days and one year

The KCCQ, EQ-5D will be summarized with means, medians, standard deviations, minimums, maximums, and interquartile ranges, at each specified time point for the attempted implant set. No statistical hypothesis test is specified.

7.10.Changes to Planned Analysis

The planned analyses in this SAP are aligned with the planned analyses noted in the CIP.

8. Validation Requirements

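### Kaplan-Meier with event-free deaths censored overstates the long-term proportion of subjects with stroke, life-threatening bleeding, endocarditis, valve thrombosis, repeat procedure or rehospitalization

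*SAP*

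**What the plan says.** SAP 7.2 applies the product-limit estimate to every time-to-event variable, at 30 days, 1 year and yearly to day 3650, and calls the results event rates. For subjects without an event, "the date of censoring will be the latest date of all follow-up visits, assessments, and events (including death". Numbers at risk, numbers with events and 95% confidence intervals accompany each estimate.

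SAP 7.9.3 then specifies Kaplan-Meier rates for outcomes 2 and 5 to 10. For outcomes 5 to 10: "Event rate estimates will be provided at 30 days, 1 year and annually thereafter up to 10 years for the attempted implant set". A typical heading is "Repeat hospitalization for aortic valve disease at 30 days, one year, and annually through 10 years". Outcome 2, all stroke, starts at 1 year and also runs to year 10.

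SAP 7.4 adds: "In time-to-event outcomes drop-outs will be censored at the time of discontinuation, consistent with the Kaplan-Meier approach". Protocol 12.7 names the same estimator: "A Kaplan-Meier estimate will be performed for time-to-event analysis". SAP 7.10 states: "The planned analyses in this SAP are aligned with the planned analyses noted in the CIP".

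Protocol Appendix V includes some deaths within the events. A stroke qualifies if "the neurological deficit results in death", and life-threatening bleeding includes "Fatal bleeding". Neither document mentions competing risks or a cumulative incidence function, or says what quantity the long-term rates are meant to estimate.

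**The concern.** Ordinary censoring assumes that the subject could still have the event later, unobserved. That is reasonable for someone lost to follow-up. A subject who has died cannot have a first stroke or a repeat procedure. Censoring at death removes that subject from the risk set and gives their share of the probability to the survivors, as though the dead would have had events at the survivors' rate.

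The outcomes run for 10 years in subjects aged 60 or older with no upper age limit, so deaths before the event are to be expected. A rate for the attempted implant set is naturally read as the proportion of those 150 subjects who had the event. On that reading all seven outcomes carry an upward bias that grows with follow-up and that the confidence intervals do not reflect. The study is descriptive, so these estimates are themselves the result, and SAP section 3 says the final report with long-term safety data will be submitted.

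**Working it through.** **Plan's own figures.** The documents state no 10-year event or mortality rate, so there is no figure on this point to reproduce. The only precision calculation, SAP Table 2, concerns the primary endpoints. It does reproduce: the exact intervals are 0.73 to 6.69% for 4/150 and 89.76 to 97.67% for 142/150.

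**Direction.** Take 33% dead by year 10, about 50 of 150, all event-free, with no losses and no earlier events. One event at that point raises one minus Kaplan-Meier by 1/100 = 1.0 point, but raises the proportion of subjects affected by only 1/150 = 0.67 points. This holds whatever the rates are. One minus Kaplan-Meier is never below the cumulative incidence, and it is above it once any event follows an event-free death.

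**Size.** From the documents: n = 150 (SAP 6.2) and t up to 10 years (SAP 7.2). Assumed: a constant event hazard h, a constant and independent hazard d of death outside the event, and no loss to follow-up.

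- One minus Kaplan-Meier, deaths censored: 1 − exp(−h·t)
- Cumulative incidence: h/(h+d) · [1 − exp(−(h+d)·t)]

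With h = 0.01 and t = 10, Kaplan-Meier gives 1 − exp(−0.10) = 9.52%. For d = 0.04 the cumulative incidence is 0.01/0.05 · [1 − exp(−0.5)] = 7.87%. Over the range of d:

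| d per year | Dead by year 10 | Kaplan-Meier | Cumulative incidence | Gap (points) | Gap × 150 | SD of Kaplan-Meier | Gap/SD |
|---|---|---|---|---|---|---|---|
| 0.02 | 18% | 9.52% | 8.64% | 0.88 | 1.3 | 2.53 | 0.35 |
| 0.04 | 33% | 9.52% | 7.87% | 1.65 | 2.5 | 2.67 | 0.62 |
| 0.06 | 45% | 9.52% | 7.19% | 2.32 | 3.5 | 2.81 | 0.83 |
| 0.08 | 55% | 9.52% | 6.59% | 2.92 | 4.4 | 3.00 | 0.97 |

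The SDs, in points, come from 20,000 simulated cohorts of 150 per row. Kaplan-Meier was never below the cumulative incidence.

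**Earlier times, h = 0.01.** At 5 years Kaplan-Meier is 4.88% against 4.64 to 4.03%, a gap of 0.23 to 0.85 points. At 1 year the gap is 0.01 to 0.04 points. At 30 days it is nil.

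**Other event patterns at 10 years, same range of d.**
- h = 0.005: gap 0.45 to 1.51 points.
- h = 0.02: gap 1.64 to 5.48 points.
- Events clustered early (4.76% at implant, then 0.5% per year): Kaplan-Meier is 1 − 0.9524·exp(−0.05) = 9.40% against 8.97 to 7.97%, a gap of 0.43 to 1.44 points.

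**Cross-check from different assumptions.** Fixing 10-year Kaplan-Meier at 10% and 10-year mortality at 20, 40 or 60% gives cumulative incidences of 9.0, 7.9 and 6.6%. The Kaplan-Meier figure is then 11, 27 or 52% too high in relative terms. In four simulated scenarios of 1,000 cohorts each (these three, and Kaplan-Meier 20% with 40% mortality), Kaplan-Meier exceeded the observed proportion in every cohort.

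**The case against.** The strongest reply is that little depends on these numbers. They are descriptive, no decision rule uses them, and in the base case the gap is under one SD of the estimate and inside its 95% interval. The death rates are assumed, and the upper end (55% dead at 10 years) has no support in the documents: subjects have a predicted 30-day surgical mortality below 3%, and a life expectancy under 24 months is an exclusion. All of that stands and limits the importance. It does not remove the bias, which is systematic and not covered by the reported interval.

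Second, Kaplan-Meier with deaths censored is a recognised summary of net risk, and the SAP names the estimator each time. The estimate is wrong only if read as a proportion of subjects. That is fair, but the plan calls it an event rate for the attempted implant set and nowhere states the net-risk reading. Equality is also possible: an outcome with no event after the first event-free death would show no gap.

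Third, numbers at risk, event counts and annual mortality are all reported, so a careful reader could notice a large divergence. This helps, but a raw count over 150 is not adjusted for loss to follow-up, and event-free deaths are not tabulated by outcome.

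Finally, censoring drop-outs under SAP 7.4 is not a fault in itself, since Aalen-Johansen censors them too. The problem lies only in giving death the same treatment.

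**Conclusion.** The concern holds. Under the stated rule, the long-term rates for outcomes 2 and 5 to 10 will exceed the proportion of treated subjects with the event once any event follows an event-free death. The direction is a property of the estimator. The size depends on assumed rates: about 0.9 to 2.9 points at 10 years in the base case, and 0.4 to 5.5 points over all the constant-hazard and early-clustering patterns tried, negligible at 1 year and nil at 30 days. Fatal strokes and fatal bleeds count as events, so only deaths outside the event contribute.

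The death-or-disabling-stroke composite, device success, all-cause mortality, the 30-day regulatory analysis and the planned primary-endpoint comparison with the Low Risk Trial TAVR arm are unaffected. The plan should be changed on this point, but it does not threaten the study's main conclusions.

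**What to change.** In SAP 7.2 and 7.9.3, for outcomes 2 and 5 to 10 at 1 year and annually thereafter:

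- Report the Aalen-Johansen cumulative incidence with its 95% confidence interval. The competing event is death that is not itself part of the outcome; fatal strokes and fatal bleeds are events.
- Add the number of subjects who died event-free beside the numbers at risk and with events.
- Keep one minus Kaplan-Meier as a supplement, labelled as the risk if death did not intervene.

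Keep Kaplan-Meier for all-cause mortality, for death or disabling stroke and for the 30-day rates. The two estimators agree at 30 days, so changing estimator from 1 year onward creates no visible break. Align Protocol 12.7, or record the departure in SAP 7.10, which now states that the SAP and protocol analyses match.

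The cost is SAP wording, one standard estimator on data already collected, a little more analysis work and slightly lower reported long-term rates. It is best settled before the long-term reports, so that the change cannot appear to be driven by the data.
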